APPENDIX A – Schedule of Events

Protocol Synopsis

Title	A Prospective Case Series Study of SPR peripheral nerve stimulation (PNS) therapy for the treatment of pain following total knee arthroplasty (TKA) utilizing preoperative lead placement
Investigational (Test) Device	The percutaneous fine-wire Smartpatch MicroLead™ that delivers electrical stimulation via connection to the SPRINT™ Peripheral Nerve Stimulation (PNS) System, an investigational external battery-powered stimulator and accessory components. Up to two leads and stimulators will be used in each subject (i.e. , 1 lead per stimulator).
Study Design	Prospective Case Series Feasibility Study
Primary Study Objective	To determine the treatment effect of PNS therapy for the treatment of knee pain following TKA
Study Plan	
Individuals undergoing a primary unilateral TKA will be considered for enrollment into the study. After obtaining informed consent, potential subjects will be evaluated for general eligibility.
 
Up to 2 weeks prior to TKA surgery, up to two leads will be placed percutaneously [REDACTED] [REDACTED]. Stimulation will be applied to determine optimal stimulus parameters and lead locations. Stimulation may be delivered up to the time of the TKA. Prior to the TKA surgery, the leads will be disconnected from the stimulators and remain indwelling (secured beneath waterproof bandages) until after the completion of the TKA surgery.
 
Following the TKA surgery [REDACTED], leads will be connected to Sprint stimulators. Stimulation will be turned on and stimulation parameters adjusted as needed [REDACTED] [REDACTED]. Subjects will receive treatment for up to 24 hours/day for up to 8 weeks [REDACTED] [REDACTED]. At the conclusion of the treatment period, the leads will be removed, and subjects will be followed until 3 months after the TKA surgery.
 
Subjects will be permitted to use analgesic medications, and analgesic usage will be recorded. For surgical anesthesia, subjects will not be allowed to receive any blocks in the upper thigh/buttocks [REDACTED] or blocks in any location using long lasting agents [REDACTED] [REDACTED]. Postoperatively, subjects will not be allowed to receive continuous regional nerve blocks.
 
Subjects will complete a daily diary recording their medication usage and “Average Pain” (Brief Pain Inventory, question 5) for each day of the treatment period. Other outcomes that will be assessed include tests of function, stimulation characteristics, surveys/questionnaires, and collection of pain scores and pain treatments.
 
Outcomes will be assessed based on the schedule of procedures (Appendix A).

Sites (N)	Up to 6 investigational sites
Subjects (N)	Up to 36 subjects

Inclusion Criteria	
 • At least 21 years old • Scheduled to undergo a primary unilateral total knee replacement procedure • Able to understand and willing to take part in study and comply with all study requirements
Exclusion Criteria	
 • Body Mass Index (BMI) > 40 kg/m² • Compromised immune system based on medical history • History of valvular heart disease • Implanted cardiac pacemaker/defibrillator or Deep Brain Stimulator • Evidence of joint or overlying skin infection of the affected limb • History of recurrent skin infections • Bleeding disorder OR INR ≥ 1.5 for those on warfarin • Confounding conditions • History of nerve damage in the affected lower limb • Allergy to skin surface electrodes and/or medical-grade adhesive tapes • Allergy to all local anesthetic agents such as lidocaine or previous reaction to anesthesia • Any other medical condition that may interfere with ability to participate in a clinical trial as determined by the Investigator • Prisoners, minors, legally incompetent people, unconscious patients, house staff, or students • Pregnant • History of substance abuse within 6 months • Potential secondary gain issues
Primary Safety Endpoint	Occurrence of device-related adverse events.
Primary Clinical Endpoint	Subjects will record average pain while walking over the last 24 hours in a daily diary using the 11-point numerical rating scale (0=no pain to 10=worst pain imaginable) of the Brief Pain Inventory – Short Form (Question 5; BPI-5). The mean of the daily scores recorded will be calculated, and the primary endpoint is the mean pain score across all subjects. The primary endpoint will be compared to historical controls (e.g., published data).
Secondary Endpoints	
Pain-related outcomes
 
 • Pain intensity over the last 24 hours as recorded as Average pain on a numerical rating scale (BPI-5) using a daily diary • Pain intensity over the last 24 hours as recorded as Average pain at rest on a numerical rating scale (BPI-5) using a daily diary • Cumulative analgesic usage

	
 • Opioid-related side effects (e.g., nausea and vomiting, constipation, urinary retention, pruritis, drowsiness, respiratory depression) 
Functional outcomes
 
■ Range of motion (ROM) ([REDACTED]
 
 ○ Number of days to achieve key milestones in affected knee (e.g., 90 degree flexion) ○ Pain scores before, during, and after ROM testing 
 • Timed Up and Go (TUG) test • 6 minute walk test (6MWT) • Fixed distance walk test 
Surveys
 
 • Change in pain, physical function, and stiffness as measured by the Western Ontario McMaster University Osteoarthritis Index (WOMAC) • Pain interference with activities of daily living as recorded on numerical rating scale (BPI-9) • Patient Global Impression of Change (PGIC) • Pain Catastrophizing Scale (PCS) • Time to meet recovery milestones (e.g., discharge date) • Subject satisfaction with the study and therapy as measured by a Subject Satisfaction Survey
Exploratory Measurements	
 • Analyses of primary and secondary endpoints at study intervals not specified in Section 3.0 • Subject-shaded diagrams of pain and paresthesia • Clinician Satisfaction Survey
Key Demographic Information	
 • Body Mass Index (BMI) ■ Surgical approach [REDACTED] • Use of post-operative drains • Type of knee implant used (i.e., manufacturer and model)

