Analgesics: Although analgesics are used both in-hospital and in the home environment after discharge, their risks of side effects and dependence make them undesirable. The primary analgesics used in multimodal pain therapy are opioids (*e.g.*, oxycontin), which carry risks of dependence and debilitating side effects that cause substantial discomfort and interfere with physical rehabilitation (*e.g.*, sedation, dizziness, nausea, gastrointestinal problems, sleeping problems) (Sinatra 2010, Strassels et al. 2005, Apfelbaum et al. 2003, Wheeler et al. 2002, Kastanias et al. 2010, Benyamin et al. 2008, Eisenberg et al. 2005). Anticonvulsants (*e.g.*, gabapentin, pregabalin) are also used in multimodal pain therapy (Andersen et al. 2009, Buvanendran et al. 2010, Clarke et al 2009) but also carry risks of side effects (sedation, dizziness, headache, blurred vision) that limit physical rehabilitation (Buvanendran et al. 2010, Clarke et al 2009, Zhang et al. 2011). Other non-opiates (NSAIDs, acetaminophen) have minimal risk of side effects but are insufficient on their own and are most often paired with other analgesics. Fear of pain medications and addiction is one of the top concerns of patients prior to TKA (Chang et al.

2004).

Regional nerve blocks: Single shot (*i.e.*, injection) and continuous blocks (*i.e.*, using a catheter) can provide relief of postoperative pain while recovering from surgery in the hospital, but they are not suitable for extended use outside the hospital. Blocks targeting mixed nerve trunks (*i.e.*, femoral, sciatic, “3-in-1”) can inhibit motor function in the lower limbs, impeding physical rehabilitation and increasing the risk of falls. Alternative approaches can avoid motor block (*i.e.*, adductor canal block, periarticular/intraarticular block) and are useful in-hospital but cannot be practically or safely delivered in the home environment. The analgesic effects of injections last for ≤ 48 hours and cannot be delivered outside the clinical setting. Continuous nerve blocks are seldom used for more than 7 days due to the risk of infection from indwelling catheters.

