3.3 Secondary Outcomes

Secondary outcome measures will provide additional information on pain and function, which will be used to aid in the design of future clinical studies.

Brief Pain Inventory-Short Form (BPI)

The BPI is a widely used assessment designed to measure pain intensity and the interference of pain on daily activities and moods (Cleeland and Ryan 1994). The BPI is recommended by the Initiative on Methods, Measurement, and Pain Assessment in Clinical Trials (IMMPACT) panel and has demonstrated validity and reliability across many cultures and languages (Cleeland and

Ryan 1994; Tan et al. 2004; Dworkin et al. 2005). The IMMPACT panel was assembled to develop consensus recommendations to improve and standardize the design and conduct of clinical trials involving treatments for pain.

Cumulative Analgesic usage

The amount and type of analgesic used by the subject will be recorded daily in a diary before TKA surgery, from the subject's records during their hospital stay, in daily diaries after discharge from the hospital, and at each visit following End of Treatment. Specific analgesic information that will be collected may include Patient Controlled Analgesia (PCA) dosage requests, PCA dosage, intravenous (IV) medications (opioids and non-opioids), oral opioids, and oral non-opioid pain medications. This information will provide an indirect measure of pain intensity, as usage of analgesics may relate to the amount of pain experienced. Narcotic usage may be converted into a morphine equivalent dosage (MED). The use of other methods of pain relief will also be recorded (e.g., cryotherapy).

Opioid Related Side Effects

Opioid pain medications are associated with a wide variety of side effects. Common side effects include nausea and vomiting, constipation, urinary retention, pruritis, drowsiness, and respiratory depression. Subjects may be questioned for each of these side effects throughout the study. Side effects from narcotic therapy will be collected but not reported as adverse events.

Range of motion

Adequate knee ROM is essential for activities of daily living but is limited by postoperative pain.. The active ROM (AROM; no assistance from clinical staff) and passive ROM (PROM; assisted by clinical staff) will be assessed during the study, and when possible the same clinical staff members at each site should take all ROM measurements to limit intertester variability.

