8.1 Analysis of Outcomes and Exploratory Measures

A table of outcomes and exploratory measures to be collected during the study can be found in Appendix A.

Question 5 of the Brief Pain Inventory-Short Form (BPI-5) is an 11-point numerical rating scale rating “Average Pain”. The BPI-5 will be measured at Visit 1 to establish a baseline score, as well as daily during stimulation and monthly post-EOT. For each subject, the mean over the first 4 weeks following TKA surgery will be calculated. An overall mean across all subjects for the first 4 weeks following TKA surgery will be calculated as well. This outcome will also be compared to historical controls (e.g., published data).

Additionally, sub-analyses will be performed to determine the mean over different post-operative phases (such as acute (e.g., days 1-7) or subacute (e.g., days 7-28)); calculate the mean for each subject and across subjects up to End of Treatment (week 6); and evaluate the proportion of subjects with pain below a certain threshold (e.g., 4/10).

Subjects will also rank their daily “Average Pain” (BPI-5) while walking. These data will undergo the same analysis as listed above for the standard BPI-5. This outcome will also be compared to historical controls (e.g., published data).

At the weekly visits during stimulation, subjects will be asked to report their weekly “Average Pain” (BPI-5) while at rest. The mean over different intervals (such as weeks 1-4 or weeks 1-6) will be calculated.

At each study visit, pain treatments and analgesic usage will be recorded. Changes in analgesic usage will be calculated using morphine equivalent dosing (MED). The usage of analgesics over various intervals (such as weekly averages, during weeks 1-4, etc.) will be calculated.

Medication usage will also be compared to pain scores to examine the correlation between analgesic usage and pain. The time to cessation of opioid will be determined. Also at each study visit, subjects will be queried for opioid related side effects. The number of effects noted over various intervals will be calculated.

Range of motion [REDACTED] will be collected at visits before, during, and after treatment. The time to achieve milestones (e.g., 90 degrees flexion, 100 degrees flexion) will be calculated for each subject and across all subjects. The mean flexion, extension, and range of motion (flexion – extension) across all subjects will be determined. The same will be calculated for passive ROM and active ROM.

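### The count of opioid-related side effects has no opioid-exposure condition, denominator or baseline reference, so it cannot be read as an opioid effect

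*Combined protocol and SAP*

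**What the plan says.** **Definition.** The Synopsis (Secondary Endpoints) gives the endpoint as a label followed by example symptoms: "Opioid-related side effects (e.g., nausea and vomiting, constipation, urinary retention, pruritis, drowsiness, respiratory depression". Sections 3.1 and 3.3 repeat the list.

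**Who is asked, and when.** Section 8.1 states: "Also at each study visit, subjects will be queried for opioid related side effects". Section 3.3 is softer: "Subjects may be questioned for each of these side effects throughout the study". The visit sections place the query among outcomes that may be assessed at Visits 1 and 2 (before surgery), each in-hospital Visit 5, Visits 6 to 10, Visit 11, and Visits 12 and 13 (2 and 3 months). It is not listed at Visits 3 or 4.

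**Summary.** Section 8.1 gives the whole analysis in one sentence: "The number of effects noted over various intervals will be calculated".

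**Attribution.** Sections 3.3 and 10.0 both say: "Side effects from narcotic therapy will be collected but not reported as adverse events". Neither says who decides that a symptom comes from a narcotic, or by what rule.

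**Exposure data.** Section 3.3 says "The amount and type of analgesic used by the subject will be recorded daily in a diary before TKA surgery", then from hospital records during the stay, from diaries after discharge, and at visits after End of Treatment. Section 8.1 adds: "At each study visit, pain treatments and analgesic usage will be recorded". These data feed morphine-equivalent summaries, a correlation with pain scores and the time to opioid cessation. No comparison with side effects is planned.

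**Other causes.** Section 2.2 says that anticonvulsants used in multimodal therapy help "but also carry risks of side effects (sedation, dizziness, headache, blurred vision) that limit physical rehabilitation". It also names urinary retention and respiratory depression as risks of epidural anesthesia. Section 6.4 permits opioid and non-opioid analgesics.

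**The concern.** The listed symptoms are common to many causes around knee surgery, and the query is not limited to subjects taking an opioid. It starts before surgery and continues to 3 months. The plan expects opioid use to end in some subjects during that time, since time to cessation is an outcome. A drowsy or constipated subject who no longer takes an opioid can therefore add to a total labelled opioid-related.

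Section 3.3 says secondary outcomes will inform the design of later studies. A total that includes symptoms unrelated to opioids would be a poor basis for an expected rate or an expected reduction. The distortion would be largest in late intervals, when the fewest subjects are likely to be on opioids.

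**Working it through.** **1. Figure to reproduce.** There is none. The documents give no expected rate, precision or test for this endpoint.

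**2. What an opioid reading would need, checked against the text.**

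| Element | Found? |
|---|---|
| Opioid use in the period asked about | Not in the Synopsis, 3.3 or 8.1 |
| Rule for attributing cause | Implied by the wording in 3.3 and 10.0; no rule given |
| Denominator (subjects, queries or time on opioid) | Not in 8.1, which plans a number of effects |
| Baseline reference | Asked at Visit 1 (6.5.1); not used in 8.1 |

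**3. Opportunities to be counted** (from 6.5.1 to 6.5.8). Visit 1, Visit 2, at least one Visit 5, Visits 6 to 10, 11, 12 and 13: 1 + 1 + 1 + 5 + 1 + 1 + 1 = 11 or more per subject. For 36 subjects, 36 × 11 = 396. Two of the 11 precede surgery. Visit 5 is daily, so each extra hospital day adds a query, and each missed visit removes one. A count without a denominator moves with length of stay and attendance as well as with symptoms.

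**4. Illustration of size. All rates and user numbers are assumptions.** Let 36 subjects answer one query, each contributing at most one symptom. Let 40% of opioid users and 15% (range 5% to 25%) of non-users report a symptom.

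Count = users × 0.40 + non-users × non-user rate.

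- 9 users, 27 non-users: 9 × 0.40 = 3.6 and 27 × 0.15 = 4.05, total 7.65. Non-user share 4.05/7.65 = 53%. At 5%: 1.35/4.95 = 27%. At 25%: 6.75/10.35 = 65%.
- 2 users, 34 non-users: 2 × 0.40 = 0.8 and 34 × 0.15 = 5.1, total 5.9. Non-user share 5.1/5.9 = 86%. At 5%: 1.7/2.5 = 68%. At 25%: 8.5/9.3 = 91%.

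These shares depend only on the ratio r of the non-user rate to the user rate: 27r/(9 + 27r) and 34r/(2 + 34r). Holding 40% fixed and moving the other rate covers r from 0.05/0.40 = 0.125 to 0.25/0.40 = 0.625.

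**5. How the count tracks opioid use.** The background rate applies to users too, so the excess in users is users × (0.40 − 0.15). Going from 9 users to 2, it falls from 9 × 0.25 = 2.25 to 2 × 0.25 = 0.5, or 78%. The planned count falls from 7.65 to 5.9, or 23%. At a 5% background the count falls from 4.95 to 2.5 (49%), and at 25% from 10.35 to 9.3 (10%).

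**6. Exposure is not cause.** On the same assumptions, 0.15/0.40 = 37.5% (range 0.05/0.40 = 12.5% to 0.25/0.40 = 62.5%) of symptoms in users are background. Restricting the count to users would remove part of the problem only.

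**The case against.** The strongest reply is that the wording already implies a judgement of cause: staff ask about opioid-related effects, and what is collected is described as coming from narcotic therapy. The case report form, which might record cause or current opioid use, is not in the documents. A reader might infer that every listed symptom is scored as opioid harm at every visit. The documents do not support that: the scoring is not stated, 3.3 and the visit sections say the query may be made, and Visits 3 and 4 omit it. What stands is that an unstated judgement at up to 6 sites is not a rule, so the count is not reproducible on either reading.

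A reader might also infer that the plan will hide a reduction in opioid harm produced by stimulation. No such contrast is planned. Historical comparison is specified for pain scores only, and 3.3 describes secondary outcomes as additional information.

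A third tempting inference is that adverse events are being lost, because narcotic side effects are kept out of adverse event reporting. That could follow from a wrong label, but nothing shows that symptoms of other origin are so labelled.

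The evidence on other causes is also limited. Section 2.2 is general background and does not say that study subjects receive anticonvulsants; of the effects quoted from it, only sedation matches the endpoint list. Finally, analgesic use is recorded alongside the symptoms, so a cross-tabulation would be possible even without a plan change. That makes the gap easy to close; it does not make the stated summary interpretable.

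**Conclusion.** The point holds in a limited form. As written, the endpoint is a symptom list summarised as a raw count, with no exposure condition, denominator or baseline reference. Symptoms unrelated to opioids can enter it, so the count cannot be interpreted as an opioid effect.

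The size is unknown because the documents give no symptom rates. The illustrative shares (53% with 9 users, 86% with 2) rest wholly on assumed rates and user numbers. Only the direction is general: if non-users report any listed symptoms, some of the count does not depend on opioid use, and that part grows as users become fewer.

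This is one descriptive secondary outcome, with no planned test, in a feasibility series of up to 36 subjects. Priority is low to moderate.

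**What to change.** In 3.3 and 8.1, replace the raw count with the following for each interval:

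- The proportion of queried subjects with each symptom, separately for those with and without recorded opioid use in a stated look-back window. The window should match the period the query asks about, which the readable text does not give.
- The proportion of all queried subjects with both opioid use and a symptom.
- The Visit 1 level as background (taken at Visit 2 where 6.5.1 allows the assessment to move).

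Take exposure from the diary or hospital record up to End of Treatment, and from the visit medication record afterwards. Call a symptom in an exposed subject a 'symptom while on opioid'; do not assume that the opioid caused it.

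The cost is wording and a merge of data already collected. There are three small downsides. Records with missing medication data must be shown as 'opioid use unknown'. Exposure after End of Treatment rests on visit-level recall. Late on-opioid groups may be very small: with 2 users the only possible proportions are 0%, 50% and 100%, so numerators and denominators should be printed beside the percentages.

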1.0 GENERAL INFORMATION

1.1 Title of Investigation

A Prospective Case Series Study of SPR peripheral nerve stimulation (PNS) therapy for the treatment of pain following total knee arthroplasty (TKA) utilizing preoperative lead placement

1.3 Materials

The SPRINT™ Peripheral Nerve Stimulation (PNS) System

Up to two Sprint Systems will be used by each subject (i.e., 1 lead per stimulator).

1.4 Indications for Use

The Sprint System is indicated for use for the symptomatic relief and management of knee pain following total knee arthroplasty.

1.5 Study Objective

To determine the treatment effect and safety of PNS therapy for the treatment of knee pain following TKA.

2.0 INTRODUCTION AND BACKGROUND

2.1 Introduction

The goal of this research is to gather data regarding the safety and effectiveness of the SPRINT™ PNS System for the treatment of pain following total knee arthroplasty (TKA; a.k.a. total knee replacement). In 2010, approximately 719,000 TKA procedures were performed in the U.S. to treat disabling knee conditions (e.g., osteoarthritis), and this number is expected to grow to 3.5 million procedures per year by 2030 (Center for Disease Control, 2010, Kurtz et al. 2007). However, a large proportion of TKA patients continue to have poor function for months after surgery. This leads to reduced quality of life (QoL), productivity, and independence. One of the primary causes is postoperative pain, which inhibits early rehabilitation and can lead to chronic pain (Capdevila et al. 1999, Peters et al. 2007, Puolakka et al. 2010, Sinatra 2010).

Approximately half (30-90%) (Anderson et al. 2009, Dahlen et al. 2006, Strassels et al. 2004, Choy et al. 2011, Brander et al 2003) of all patients experience moderate to severe pain during the first 2 months after TKA surgery, and prolonged postoperative pain decreases QoL (Chelly et al. 2001, Forrest et al. 1999, Ilfeld et al. 2007, Liu et al. 2012, Mahoney et al. 1990, Panel 1997, Sinatra 2010, Strassels et al. 2004, Wang et al. 2002).

Postoperative pain greatly reduces patient comfort and increases the use of opioids and the length of hospital stay, which increases medical costs (Panel 1997; Rosenquist and Lederhaas 1999; Chelly et al. 2001; Wang et al. 2002). Also, postoperative pain limits knee range of motion and patient tolerance of rehabilitation exercises, which delays return to normal functioning (Shoji et al. 1990; Ryu et al. 1993; Dahlen et al. 2006; Reuben et al. 2008). In addition, uncontrolled acute pain can lead to chronic pain.

Existing treatments for postoperative pain include analgesics, continuous passive motion, cooling pads, epidural analgesia, and regional nerve blocks (anesthetic delivered continuously through a percutaneously placed catheter or as single injections). In spite of these treatments, most patients experience moderate to severe acute pain. Further, during the subacute phase, these treatments are ineffective, are not indicated for such an extended period of time or for at home use, and/or carry risks of side effects and complications. As a result, a non-opioid treatment is needed that can relieve postoperative pain following TKA with minimal side effects and can be used throughout the duration of the subacute phase. The proposed study will determine the feasibility of using PNS therapy to treat postoperative pain following TKA. The hypothesis is that percutaneous stimulation will evoke a [REDACTED] sensation [REDACTED] in the region of pain and produce clinically significant reductions in pain.

Subjects will receive leads to stimulate the nerves innervating the regions of pain or expected pain [REDACTED] up to 2 weeks prior to TKA surgery. Stimulation may be delivered up to the time of the TKA. Following TKA, stimulation will be turned on and adjusted as needed to provide pain relief. Subjects will record average pain over the last 24 hours in a daily diary using the 11-point numerical rating scale (0=no pain to 10=worst pain imaginable) of the Brief Pain Inventory – Short Form (Question 5; BPI-5). The mean of the daily scores recorded from POD0 to POD28 (i.e., first 4 weeks following TKA surgery) will be calculated, and the primary endpoint is the mean pain score across all subjects, which will be compared to historical controls (e.g., published data). Subjects will receive treatment for up to 24 hours/day for up to 60 days (i.e., leads will be indwelling for up to 60 days total). Subjects will be followed for three months following TKA surgery. The results of this study will [REDACTED] will be used to support subsequent studies of the SPR PNS therapy to treat postoperative pain following TKA.

